Traditional suture-based fixation is known to cause significant patient discomfort, predominantly at the site of skin suture fixation, where any pull on the drain tubing is transmitted to a focal point on the skin. Over time, this can result in significant skin irritation, inflammation and pain, skin erosion, loosening of the drain, suture failure, and possibly even early, unintended loss of the drain. Early loss of a drain, in turn, can lead to complications of seroma and/or infected abscess. In a survey of 40 Wake Forest Plastic Surgery Patients with drains, patients asked were to rate their experience with surgical drains compared to their expectations on a sliding scale. The majority of patients reported experiences that were worse than or as expected (Figure 1). When specifically asked about irritation at the drain site, 33 of 40 patients rated comfort and pain as worse than

or as expected (Figure 2). With the known negative patient experiences associated with suture-based drain securement, there is a need for novel drain securement techniques and devices that can improve patient comfort and drain security.

The K-Lock® Device is a novel sutureless drain securement device that may improve patient experiences with surgical drains. The K-Lock Device is an FDA Class I device exempt from 510k requirements.

OBJECTIVES:

To evaluate the feasibility, safety and efficacy of a novel suture-less drain securement device (K-Lock) via direct comparison to suture-based techniques.

To evaluate patient satisfaction with their surgical drain sites post operatively.

DESIGN:

Randomized controlled trial

SETTING:

Academic Medical Center

SUBJECTS SELECTION CRITERIA:

Inclusion Criteria:

Age 18 or older

Patient of the Department of Plastic and Reconstructive Surgery

Able to sign English language Consent form

Undergoing any of the following procedures requiring placement of 2 or more drains (preferably bilateral) including:

- Breast reconstruction
- Bilateral Breast Reduction
- Abdominoplasty
- Body Contour surgery (e.g. panniculectomy, brachiplasty, thighplasty)

Exclusion Criteria:

Patients with unilateral drain placement Unable to sign English language consent form Allergy to Tegaderm Dressing Allergy to skin adhesives

SAMPLE SIZE:

We plan to enroll 40 patients allowing analysis of 80 (20 paired) drain sites: 40 prototype drain securement sites and 40 suture-based drain securement sites.

INTERVENTIONS AND INTERACTIONS:

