Patients will be randomized to either A) left side K-Lock with right side suture-based technique or B) right side K-Lock with left side suture-based technique. Randomization will occur before study initiation with group A or group B being assigned to a study enrollment number.

Preoperatively:

The novel suture-less prototype device will be described and/or demonstrated to the patients, and the rationale for its development will be explained. They will have opportunity to ask questions and then they will be invited to participate in the study.

Written informed consent will be obtained.

Intraoperatively:

Surgical drains will be placed per the usual routine of the surgeon. However, prior to definitive fixation, the drains will be temporarily secured to the skin with a towel clamp and covered and/or positioned out of the way to allow for closure of surgical incisions. Definitive drain fixation will occur when all of the pertinent incisions are closed and dressed. At that time, each drain will be secured according to the randomization scheme.

The amount of **time it takes to secure and dress each drain will be recorded** using a time-stamped video (e.g. iphone). No identifying data/information will be recorded, only the zoomed field pertinent to drain securement. For the prototype drain securement device, the 'video clock' will be started when the device is passed to the surgeon and stopped when the device/dressing is attached in place. For the standard suture-based technique, the 'video clock' will be started when the suture is passed to the surgeon and will be stopped when the dressing has been placed and secured. Use of a Biopatch with the drain will be up to the surgeon's preference. The standard dressing for the suture-based techniques will include a split 4 x 4 dressing covered with a tegaderm. All dressing materials must be ready and available prior to handing the surgeon the suture/device.

Postoperatively:

The time until drain removal will be recorded for both groups.

On postoperative visit(s) on which a drain is removed, patients will complete a **survey** about their experience with the pertinent securement method/drain site.

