Feasibility and **ease of use** of the novel drain device will be evaluated by evaluation of video recordings, qualitative feedback obtained from surgeons and/or O.R staff and nurses that handle and observe use of the device. Any failed application of the device will specifically be noted. In the event that a test device will need to be replaced for continued drain securement because the device has become loose or otherwise fouled, the replacement process will be performed by clinic staff using the IFU for such, and will be video recorded

Safety of the novel drain device will be evaluated by inspecting device sites for instances of skin irritation at each office visit and at the time of drain removal, including photographs of drain sites immediately before and after removal. It will also be assessed by feedback obtained in the patient surveys.

Postoperative review of patient charts will collect the following information up to 1 month from the removal of a subject's final drain:

- Date of drain removal (i.e. duration of drain)
- Accidental vs Planned drain removal
- Loosening of the drain
- Any need for new device/new suture material to secure drain
- Reinsertion of drain
- Patient calls to triage regarding drain issues/concerns and the estimated or actual time/effort devoted to each issue/concern by clinic staff
- Photos of the drain site at time of removal

As a follow-up to previous study activities, subjects will be contacted either by phone or at future clinic visits to gauge their interest in further participation. Subjects will be asked to have pictures taken of their drain sites and to fill out a survey to measure their satisfaction with their surgical drain sites further out from their procedures. Pictures will be attained at a scheduled research visit or a regular clinic visit if possible. A blinded evaluator will view the photos to assess in addition to the subject's self-reported outcomes. The tool the subjects will complete is the Patient and Observer Scar Assessment Scale (POSAS).

OUTCOME MEASURES:

Primary:

Feasibility

Secondary:

Safety

Satisfaction

ANALYTICAL PLAN:

Results will be analyzed initially using descriptive statistics. Comparison between groups will be done using chi square tests for proportions, and t-tests or ANOVA procedures for continuous variables. Regression analysis will be performed to identify independent outcome predictors. Other inferential statistical analysis will be conducted as appropriate.

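### An unspecified search for independent predictors on 40 patients, with no provision for paired sites, carries a material risk of chance findings and should give way to a pre-stated paired model

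*Combined protocol and SAP*

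**What the plan says.** The regression is one sentence in the Analytical Plan: "Regression analysis will be performed to identify independent outcome predictors". The sentence after it is open-ended: "Other inferential statistical analysis will be conducted as appropriate". The tests named before it are chi-square tests, t-tests and ANOVA. Pairing is not mentioned there.

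The design is within-patient. Under Interventions and Interactions, group A receives "left side K-Lock with right side suture-based technique" and group B the reverse, so every patient has both methods. The Sample Size section reads "We plan to enroll 40 patients allowing analysis of 80 (20 paired) drain sites", made up of "40 prototype drain securement sites and 40 suture-based drain securement sites".

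The Objectives are a direct comparison of K-Lock with suture (feasibility, safety, efficacy) and patient satisfaction with the drain sites. Predictors appear in neither. Outcomes are of mixed type: securement time, drain duration, survey and scar scores, and binary items such as "Accidental vs Planned drain removal". No expected event rate is given for any of them.

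**The concern.** The plan commits to finding independent predictors without saying of what, from which candidates, or by which model. Factors such as age or procedure vary between patients only, so 40 patients supply 40 independent values however many sites are analysed. Nothing in the plan prevents the 80 sites from being entered as 80 independent records, which would make standard errors for patient-level factors too small.

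At stake is a report that names a patient characteristic as an independent predictor of drain problems or satisfaction when the association is chance. The search is also not needed for the trial's main question. The paired design already balances patient characteristics between methods, and an analysis that uses the pairing answers that question more precisely.

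**Working it through.** **Inputs from the documents.** 40 patients, two sites each: 40 × 2 = 80 sites, 40 per method, which matches the stated total. One left-right pair per patient gives 40 pairs, not the 20 printed in the Sample Size section. That is a separate point to reconcile; 40 pairs are used here. The plan gives no alpha, power, effect size or event rate, so there is no figure of its own to reproduce beyond this count.

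**Assumptions.** Two-sided 5% tests; 6, 8 or 10 patient-level candidates; no real predictor; continuous outcome; within-patient correlation 0.5 where sites are used.

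**1. Independent-tests guide.** P(at least one false) = 1 − 0.95^k.
- k = 6: 1 − 0.735 = 26.5%
- k = 8: 33.7%
- k = 10: 40.1%
- For comparison, k = 1: 5%; k = 3: 14.3%

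**2. Simulation on 40 patients.**
- Full model, no selection: about 23–38% over 6 to 10 candidates. A 4,000-run check gave 26%, 30% and 35% for 6, 8 and 10.
- Backward elimination at 5%: 27%, 34% and 43%. Other runs differed by no more than about 3 points.

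**3. The 80 sites treated as independent.** For a patient-level covariate the variance is understated by the factor 1 + (2 − 1) × 0.5 = 1.5. The effective critical value is 1.96/√1.5 = 1.60, so the true error per test is about 11% instead of 5%. Then 1 − 0.89^k gives 50%, 61% and 69% for k = 6, 8 and 10. Simulation with backward elimination gives 51%, 62% and 71%.

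All these rates are per outcome.

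**4. Binary outcomes (conditional).** Events among 80 sites are 80 × rate: 4 at 5%, 8 at 10%, 16 at 20%, 24 at 30%. With 8 candidates that is 0.5, 1, 2 and 3 events per candidate. In null logistic models on 80 sites with 5 to 10 candidates, 45–74% failed to converge or separated at a 5% rate, 15–30% at 10%, and about 2% at 20%. Low rates did not raise the false-positive rate. Among models that fitted, at least one Wald test was significant in 10–19% at a 5% rate, against 19–39% at 20%.

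**5. What a paired model offers.** Take a true difference of 0.5 SD and correlation 0.5.
- Paired: SE = √(2 × (1 − 0.5)/40) = 0.158 SD and 0.5/0.158 = 3.16, so power is about 0.87.
- Unpaired t-test on the same data: its assumed SE is √(2/40) = 0.224, so it needs a difference of about 1.99 × 0.224 = 0.445. The true SE is still 0.158, so power = P(Z > (0.445 − 0.5)/0.158) = P(Z > −0.35), about 0.63–0.64.
- A model with patient, method and side leaves 80 − 40 − 2 = 38 residual degrees of freedom.

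**6. Limit of the paired model for binary outcomes.** At a 10% rate for both methods, expected discordant pairs are 40 × 2 × 0.10 × 0.90 = 7.2 with no within-patient correlation, and half that, 3.6, at correlation 0.5. Matched logistic regression with method and side, 20 patients per sequence, is then non-estimable in about 50% and 88% of data sets. Exact McNemar for method alone can always be computed. Its smallest two-sided p-value with n discordant pairs is 2 × 0.5^n: 0.0625 for n = 5 and 0.031 for n = 6. With fewer than six discordant pairs it cannot reach 5%.

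**The case against.** The strongest reply is that the sentence is merely under-specified. It does not mention stepwise selection, and one fixed model with a few covariates would satisfy it. With one or three pre-stated predictors the risk is only 5% or about 14%. The plan names no candidates. Securement method, body side and Biopatch use can be site-level, and the argument from 40 independent values does not apply to them. If method is in the model, the regression is an adjusted device comparison and not irrelevant to the trial's question. All of this stands. It is why the percentages are conditional, and why keeping a short exploratory list is acceptable.

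Four stronger readings are tempting and are not supported:
- **That events are rare.** No rate is stated. The Background says only "possibly even early, unintended loss of the drain", which is not a figure. The one outcome frequency given, 33 of 40 patients in an earlier survey rating comfort and pain as no better than expected, is common. Several outcomes are not events at all.
- **That rarity produces the false predictors.** Step 4 shows otherwise: it produces instability. The number of candidates, selection and ignored pairing produce false positives.
- **That most reported predictors will be false.** The calculation gives the chance of at least one false predictor when none is real. The share of reported predictors that are false depends on how many real ones exist, which is unknown.
- **That the device comparison is compromised.** The regression sentence does not determine it. The primary outcome is feasibility, and results are first analysed descriptively.

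**Conclusion.** The point holds as one of specification and pairing. The plan commits, without an exploratory label, to a predictor search that no objective requests, on 40 patients, with nothing that accounts for two sites per patient. With 6 to 10 patient-level candidates and none real, the risk of at least one false predictor per outcome is roughly a quarter to two-fifths when analysed at patient level. It is half to seven-tenths with backward selection if sites are treated as independent at correlation 0.5. These figures rest on assumed candidate numbers, selection rule and correlation, and fall sharply with one to three pre-stated factors. Instability of binary models is a further concern only if those outcomes prove uncommon. The effect on the trial's main conclusion is limited. The change is worth making because it is cheap and brings the analysis into line with the design.

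**What to change.** Replace the regression sentence in the Analytical Plan with the following.

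- **Continuous outcomes.** Name the main ones, for example securement time and the survey score. For each, state one model with securement method and body side as fixed effects, patient as the matching or random factor, and no variable selection.
- **Binary outcomes.** Compare methods within patient by exact McNemar, method alone, and report the discordant counts. Do not add side to a matched logistic model, because it is often non-estimable with few discordant pairs. State that few discordant pairs also limit what McNemar can show.
- **Patient factors.** If wanted, give a short list in advance, analyse at patient level (for example on patient means), label the results exploratory, and make no claim of an independent predictor.

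The cost is a few sentences of text and an exploratory output given up or downgraded. No extra patients or data are needed. Deleting all analysis of patient factors would also remove the risk, but it is not required.
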